- a: Visit 3 should be conducted 7 to 10 days after completion of the Baseline visit (Visit 2) assessments and confirmation of eligibility to continue in the study, unless additional time is required to take Exclusion Criterion #19 into account. A window of ± 3 days will be permitted for Visit 4 to 14 inclusive. A window of ± 10 days will be permitted for Visit 15 to 18 inclusive. A window of ± 3 days will be permitted for the Follow-Up Visits. If use is made of the permitted visit windows, every effort should be made to bring the subject back in line with the "weeks elapsed since first dose" at subsequent visits.
- b: Subjects who discontinue taking study drug prematurely for any reason will undergo an ED Visit within 7 days of their last dose of study drug. In addition, Follow-Up Visits will be scheduled 4 and 12 weeks after the last dose of study drug (Visit 19 and Visit 20, respectively). Subjects who discontinue study drug prematurely will also be scheduled to return to the study site for each scheduled visit when clinical efficacy assessments are to be conducted (ie. at Visits 11, 14, 15, 16, 17, and 18, if these visits have not already been performed). At these visits, only clinical efficacy assessments (MMSE, CDR, ADAS-cog₁₄, FAQ, CBB, and ISLT) will be conducted. Regularly scheduled clinical efficacy visits do not need to be attended if they fall within 8 days (visit window) after the Early Discontinuation Visit or within ± 8 days of either of the Follow-Up Visits (Visit 19 and Visit 20). Subjects who discontinue early from study drug are considered on study as long as they return for their regularly scheduled clinical efficacy visits as outlined above.
- c: All subjects, regardless of whether they complete all 18 months of treatment or discontinue study drug prematurely, will complete 2 posttreatment Follow-Up visits; one 4 weeks after the last dose of study drug and a second 12 weeks after the last dose of study drug (Visit 19 and Visit 20 respectively). If clinically indicated, more frequent safety assessments can be made as UNS assessments or visits during the posttreatment Follow-Up period.

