- d: Unscheduled visits may be conducted at any time that safety or safety MRI data indicate per protocol or as clinically indicated in the judgment of the investigator. Note that not all assessments indicated under UNS Visits need be conducted – actual assessments needed will be determined by the investigator and will be based on the specific visit needs.
- e: Only if clinically significant abnormalities are found at Visit 19 and the investigator considers it necessary to repeat at Visit 20. However, lymphocyte subsets and Igs should be repeated at Visit 20 if they were outside of the normal range (regardless of clinical significance) at Visit 19.
- f: Measurements of body temperature and sitting blood pressure and heart rate will be obtained.
- g: Centralized skin assessments using standardized photography will be conducted by a reviewing dermatologist. These assessments will specifically include evaluation of any areas of depigmentation or any rash. Additional UNS dermatological assessments should be conducted in response to any dermatological AEs of concern, eg, depigmentation, rash, herpetic lesion.
- h: Examples of neurological signs that may indicate new central nervous system pathology that may need further investigation include (but not limited to) visual disturbance, dysarthria, dysphasia, muscle strength, limb weakness, hyperreflexia, paraparesis, micturition difficulty or urgency or incontinence, ataxia, neuropsychiatric or cognitive decline in excess of expectations based on the subject's recent history.
- i: If the subject experiences visual disturbances during the course of the study, the subject will be referred to a specialist for a further ophthalmic examination, which should include funduscopy to look at the optic disc, macula and the rest of the retina as well as an assessment of visual acuity and visual fields
- j: Please refer to [Section 9.4.7](#), which details prohibited and permitted medications in the study and associated timeframes.
- k: 12-lead standard ECGs will be recorded in triplicate (1 minute apart).

- l: Lymphocyte subsets to be measured include CD4 [T helper cells], CD8 [cytotoxic T cells], CD19 [B cells], CD16/CD56 [NK cells] and CD14 [macrophages] and total lymphocytes. Regulatory T cells will also be measured (CD4, CD25 and CD127, FoxP3). Viability staining may also be employed.
- m: Igs to be analyzed include IgG, IgA, and IgM.

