9.7.1.8.3 LABORATORY VALUES

Laboratory results will be summarized using International System of Units, as appropriate. For all quantitative parameters listed in [Section 9.5.1.5.3](#), the actual value and the change from baseline to each postbaseline visit and to the end of treatment (defined as the last on-treatment value) will be summarized by visit and treatment group using descriptive statistics. Qualitative parameters listed in [Section 9.5.1.5.3](#) will be summarized using frequencies (number and percentage of subjects), and changes from baseline to each postbaseline visit and to end of treatment will be reported using shift tables. Percentages will be based on the number of subjects with both nonmissing baseline and relevant postbaseline results.

Laboratory test results will be assigned a low/normal/high (LNH) classification according to whether the value was below (L), within (N), or above (H) the laboratory parameter's reference range. Within-treatment comparisons for each laboratory parameter will be based on 3-by-3 tables (shift tables) that compare the baseline LNH classification to the LNH classification at each postbaseline visit and at the end of treatment. Similar shift tables will also compare the baseline LNH classification to the LNH classification for the highest and lowest value during the treatment period.

[Appendix 1](#) (Sponsor's Grading for Laboratory Values) presents the criteria that will be used to identify subjects with treatment-emergent markedly abnormal laboratory values (TEMAVs). Except for phosphate, a TEMAV is defined as a postbaseline value with an increase from baseline to a Grade of 2 or higher. For phosphate, a TEMAV was defined as a postbaseline value with an increase from baseline to a Grade of 3 or higher. When displaying the incidence of TEMAVs, each subject may be counted once in the laboratory parameter high and in the laboratory parameter low categories, as applicable.

Lymphocyte subsets (ie, CD4 [T helper cells], CD8 [cytotoxic T cells], CD19 [B cells], CD16/CD56 [natural killer cells] and CD14 [macrophages]) and regulatory T cells will be summarized in the same manner as other laboratory parameters. Mean lymphocyte subsets and the mean change from baseline in lymphocyte subsets will also be displayed graphically over time by dose.

Serum IgG, IgM, and IgA will be measured and summarized in the same manner as other laboratory parameters.

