Apolipoprotein E (*ApoE*) and *NAT2* genotyping/phenotyping will be conducted. *ApoE4* homozygous or heterozygous status and *NAT2* status will be used in the statistical analysis to determine the effects on treatment response and safety. Remaining genomic DNA may also be stored for up to 15 years to be used to examine the role of DNA sequence variability on the absorption, distribution, metabolism, and elimination of E2609, development of adverse events (AEs), as well as the underlying AD. Variations in E2609 exposure or the occurrence of AEs observed in the study population may be evaluated by correlation of single-nucleotide polymorphisms with PK, safety, or PD data.

Safety Assessments

Every effort should be made to keep the site staff responsible for reviewing laboratory reports and assessing AEs separate from the site staff responsible for the efficacy assessments. Routine safety assessments will include the monitoring and recording all AEs and serious AEs, monitoring of hematology, blood chemistry, and urinalysis, measurement of vital signs, regular ECGs, physical and neurological examinations, and dermatological

assessments at regular intervals. Information for AEs relating to abuse potential will be collected via a detailed narrative. Subjects reporting AEs relating to abnormal dreams or sleep-related events, or sleep terror will be questioned on the frequency and impact of these events.

Complete blood counts and lymphocyte subset absolute counts and percentages will be measured (by a centralized laboratory) every week for the first month, every 2 weeks for the next 2 months (Months 2 and 3) and monthly for the next 3 months (Months 4, 5, and 6). Thereafter they will be monitored every 3 months until the end of the Treatment Period and at both Follow-Up Visits. Serum IgG, IgA, and IgM will be monitored monthly for the first 3 months, at 6, 12, and 18 months, and at both Follow-Up Visits.

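### Visit 20 safety tests are taken only from subjects abnormal at Visit 19, yet the plan summarizes them by visit and arm like any other visit

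*Protocol*

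**What the plan says.** Visits 19 and 20 fall 4 and 12 weeks after the last dose; Table 7 note c describes the later one as "a second 12 weeks after the last dose of study drug (Visit 19 and Visit 20 respectively"). Table 7 marks these items at Visit 20 with note e: routine physical examination, vital signs, respiratory rate, ECG, biochemistry and urinalysis, complete blood count, lymphocyte subsets and immunoglobulins. The note gives two triggers:

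- General rule: "Only if clinically significant abnormalities are found at Visit 19 and the investigator considers it necessary to repeat at Visit 20".
- Lymphocyte subsets and immunoglobulins: "lymphocyte subsets and Igs should be repeated at Visit 20 if they were outside of the normal range (regardless of clinical significance) at Visit 19".

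The analysis text does not reflect this. Section 9.7.1.8.3 summarizes "the actual value and the change from baseline to each postbaseline visit and to the end of treatment" by visit and treatment group. It makes low/normal/high shift tables at each postbaseline visit, with percentages based on subjects who have a result. It also says that the "mean change from baseline in lymphocyte subsets will also be displayed graphically over time by dose". Sections 9.7.1.8.4 (vital signs) and 9.7.1.8.5 (ECG) present descriptive statistics by visit and treatment group. None of the three sections excepts Visit 20.

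The document holds two texts of the protocol: one that begins partway through Section 9.2.3, and one that begins with the synopsis. Both carry the conditional rule (note e in the first, note y in the second) and the same laboratory analysis section. Only the second has a synopsis. Of blood counts and lymphocyte subsets it says "Thereafter they will be monitored every 3 months until the end of the Treatment Period and at both Follow-Up Visits", and it likewise places immunoglobulins at both Follow-Up Visits, without any condition.

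**The concern.** Whether a subject has a Visit 20 value depends on that subject's Visit 19 value. For lymphocyte counts, treatment may affect the Visit 19 value. Section 7.1 reports falls in CD4, CD8 and CD19 at 200 and 400 mg in the earlier multiple-dose study, and some CD4 reduction at 50 to 100 mg; 50 mg is the top dose here. A Visit 20 mean by arm is then not a comparison of the randomized groups. It compares those who failed a screen four weeks after stopping, and the arms may fail that screen at different rates and in different directions.

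Immunological safety is part of a primary objective (Section 8.1), and dosing extends from 14 days to 18 months. The last point on the lymphocyte plot is where a reader would look for recovery 12 weeks off drug. Followed literally, the plan joins that point to the earlier ones as if the same subjects contributed.

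**Working it through.** **Step 1. Is conditional sampling really planned?** Table 8 gives the number of treatment and follow-up draws, which can be counted against Table 7.

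| Test | Treatment visits | + Visit 19 | + Visits 19 and 20 | Table 8 |
|---|---|---|---|---|
| Lymphocyte subsets | 15 (Visits 4–18) | 16 | 17 | 16 |
| Hematology | 15 | 16 | 17 | 16 |
| Chemistry | 9 | 10 | 11 | 10 |
| Immunoglobulins | 6 | 7 | 8 | 7 |
| PD sample | 6 | 7 | 8 | 8 |
| Immune-status storage | 5 | 6 | 7 | 7 |

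The four note-e tests match only with Visit 20 left out. The two tests without the condition match only with it counted. Table 8 therefore treats Visit 20 as conditional.

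**Step 2. Size if each analyte triggers its own retest.** The Protocol gives no SD, retest correlation or Visit 19 effect, so every input here is an assumption: normal values in SD units, reference range ±1.96, correlation ρ between Visits 19 and 20 of 0.6 to 0.9, drug arm shifted by d at Visit 19, full recovery by Visit 20 (true difference 0).

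- Fraction retested: p = Φ(−1.96 − d) + 1 − Φ(1.96 − d).
- Visit 20 mean of those retested: ρ × [φ(1.96 − d) − φ(−1.96 − d)] / p.

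Results:

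- d = 0: p = 0.050 and the mean is 0.
- d = −0.3: p = 0.0485 + 0.0119 = 0.0604; (0.0310 − 0.1006)/0.0604 = −1.15. Times 0.6 and 0.9, this gives −0.69 and −1.04.
- d = −0.5: p = 0.0721 + 0.0069 ≈ 0.079; (0.0194 − 0.1374)/0.079 = −1.49. Times 0.6 and 0.9, this gives −0.90 and −1.34.

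Simulation agrees (−0.69 to −1.35). About 5% of placebo and 6 to 8% of the drug arm are retested. At 125 per arm (500/4, equal allocation, no attrition) that is roughly 6 against 8 to 10 subjects. With no recovery at all, the selected difference is about −1.0 to −1.85 SD against a true −0.3 to −0.5 SD.

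**Step 3. Size if any out-of-range subset triggers the whole panel.** Note e speaks of the subsets together, and Table 8 shows one 4 mL draw. Take six analytes from note l (CD4, CD8, CD19, CD16/CD56, CD14, total lymphocytes), inter-analyte correlation 0 to 0.5, ρ 0.6 to 0.9, and CD4, CD8 and CD19 shifted by −0.3 to −0.5. Simulation with full recovery gives 21 to 27% of placebo and 23 to 33% of the drug arm retested, with a spurious difference of −0.11 to −0.40 SD in a shifted analyte. If all six are shifted, it reaches −0.54.

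**Step 4. No Visit 19 effect.** With d = 0 the selected difference is 0 under both triggers.

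These figures ignore the exclusion at entry of subjects with CD4, CD8 or CD19 below the lower limit of normal, which would move them. They show direction and order of size and are not estimates.

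**The case against.** The case on the other side is substantial, and most of it limits the point without removing it.

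- **The Visit 19 comparison is sound.** It is sampled in everyone, four weeks off drug. Section 7.1 says that counts in the earlier study resolved between 6 and 21 days after the last dose. If that holds here, the arms may be equal at Visit 19 and the Visit 20 bias is nil. This stands, although that study dosed for 14 days and this one doses for 18 months.
- **The assumed Visit 19 shift has no source.** This stands. At 100 mg, whose exposure exceeds that of the 50 mg tablet, CD4 fell 3.1% on drug by Day 15 (placebo rose 8.7%). Nothing is stated for four weeks after stopping.
- **The summaries are descriptive.** No test, claim or decision rule uses Visit 20. This stands.
- **Display rules usually belong in the SAP.** This answers only in part: the Protocol itself fixes a summary at every postbaseline visit, and its own schedule cannot support that at Visit 20.

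Three stronger readings are tempting. A reader might infer that subjects who become low after a normal Visit 19 are never measured; notes c and d allow unscheduled assessments if clinically indicated, so they are only not measured on schedule. A reader might infer that reversibility cannot be assessed; Visit 19 assesses it at four weeks. A reader might set the synopsis against note e directly; the synopsis belongs to the other protocol text, so the conflict can be claimed only within that text.

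**Conclusion.** The point holds as a mismatch between schedule and analysis. Visit 20 values for note-e parameters come from an outcome-selected subset, and the by-visit, by-arm summaries, laboratory shift tables and lymphocyte plot treat them as a full visit. That part needs no assumption; it follows from note e, the Table 8 counts and Sections 9.7.1.8.3 to 9.7.1.8.5.

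Bias between arms is conditional on the drug still affecting counts at Visit 19. Given a 0.3 to 0.5 SD shift there and full recovery by Visit 20, the spurious difference is about 0.7 to 1.35 SD under single-analyte triggering and about 0.1 to 0.4 SD under panel triggering with three of six subsets affected. It is zero if the arms are equal at Visit 19. A reader might conclude that the plot will show a false persistent deficit on drug; the Protocol does not support that, only that it could. The damage is confined to the descriptive 12-week off-drug readout.

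**What to change.** Add one sentence to Sections 9.7.1.8.3 to 9.7.1.8.5: for every parameter collected under note e, Visit 20 is excluded from the by-visit, by-arm means and changes, the shift tables and the lymphocyte plot. Report Visit 20 only as follow-up of Visit 19 abnormalities, by arm: number abnormal out of all subjects sampled at Visit 19, number retested, and number resolved. For parameters under the general rule, number retested also shows how often the investigator chose to repeat. This costs one sentence and one small table, with no new data.

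Separately, in the protocol text that carries the synopsis, the statement that blood counts, lymphocyte subsets and immunoglobulins are monitored at both Follow-Up Visits must be reconciled with the conditional Table 7 note (note y there). Which schedule applies is for the sponsor to settle; the analysis sentence should then match it.

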9.5.2.2 Description of Procedures/Assessments Schedule

Please refer to [Table 6](#) and [Table 7](#) for the timings of the procedures and assessments to be performed during the study. Screening assessments will be organized into 4 tiers (see [Table 6](#), [Section 9.1.1.1](#), and [Figure 2](#)).

See [Section 9.5.1](#) for a full description of the procedures and assessments to be performed during this study.

Table 8 presents the number of blood and CSF samples, and the total volume of blood and CSF that will be collected throughout the study. Additional samples may be taken at the discretion of the investigator if the results of any tests fall outside reference ranges or if clinical symptoms necessitate testing to ensure subject safety.

Table 8 Summary of Blood and CSF Sample Volumes

| Assessment | Total number of collection time points | Number of time points x volume per collection (mL whole blood or CSF) | | Total volume (mL whole blood or CSF) |
|--|--|---|---------------------------------|--------------------------------------|
| | | Screening and Baseline Periods | Treatment and Follow-Up Periods | |
| Blood | | | | |
| Chemistry | 12 | 2 x 2 mL | 10 x 2 mL | 24 mL |
| Hematology | 18 | 2 x 5 mL | 16 x 5 mL | 90 mL |
| Lymphocyte subset analyses | 18 | 2 x 4 mL | 16 x 4 mL | 72 mL |
| PBMC | 4 | 1 x 16 mL | 3 x 16 mL | 64 mL |
| IgA, IgM, IgG | 9 | 2 x 2 mL | 7 x 2 mL | 18 mL |
| PT, PTT for INR | 2 | 2 x 3 mL | None | 6 mL |
| Thyroid function tests (thyroid stimulating hormone, free triiodothyronine and free thyroxine) | 1 | 1 x 3 mL | None | 3 mL |
| Viral screen (Hepatitis B and C) | 1 | 1 x 4 mL | None | 4 mL |
| Viral characterization | 1 | 1 x 4 mL | None | 4 mL |
| Vitamin B12 | 1 | 1 x 2 mL | None | 2 mL |
| Serum pregnancy test | 1 | 1 x 2 mL | None | 2 mL |
| Tuberculosis (interferon-gamma release assays) | 1 | 1 x 3 mL | None | 3 mL |
| Sample for immune status | 8 | 1 x 4 mL | 7 x 4 mL | 32 mL |
| PD sample | 9 | 1 x 4 mL | 8 x 4 mL | 36 mL |
| PK analysis | 7 | 1 x 3 mL | 6 x 6 mL | 39 mL |
| Pharmacogenetic sample | 1 | 1 x 3 mL | None | 3 mL |
| All blood samples, total volume whole blood collected | | 80 mL | 322 mL | 402 mL |
| CSF | | | | |
| PD and PK samples | 3 | 1 x 12 mL | 2 x 12 mL | 36 mL |

CSF = cerebrospinal fluid, Ig = immunoglobulin, INR = International Normalized Ratio, PBMC = peripheral blood mononuclear cell, PD = pharmacodynamics, PK = pharmacokinetic, PT = prothrombin time, PTT = partial thromboplastin time.

9.5.3 Appropriateness of Measurements

All clinical assessments are standard measurements commonly used in studies of AD.

Standard safety assessments incorporated into this protocol include vital signs, clinical laboratory assessments, physical examinations, ECG measurements, and reports of AEs. MRI will be used to detect vasogenic edema, macrohemorrhage, an area of superficial siderosis, or a symptomatic microhemorrhage and is a standard evaluation to ensure subject safety. The C-SSRS has been endorsed by the FDA as a measure of potential suicidality ([Guidance for Industry Suicidality](#)).

A number of safety aspects have been built into the design of this study in light of the preclinical and clinical safety data with E2609, in addition to mitigating clinical risk in the progression from 14 days of dosing in the MAD study to 18 months of treatment in this Phase 2 study. Details are provided in [Section 9.2.6](#).

9.5.4 Reporting of Serious Adverse Events, Pregnancy, and Events Associated with Special Situations

9.5.4.1 Reporting of Serious Adverse Events

All SAEs, regardless of their relationship to study treatment, must be reported on a completed SAE form by email or fax as soon as possible but no later than 24 hours from when the investigator becomes aware of the event.

SAEs, regardless of causality assessment, must be collected up to 3 months after the last dose of study drug, ie, through to the second follow-up visit (Visit 20). In subjects who discontinue study drug early, but continue with efficacy assessments, SAEs only need to be solicited up to 3 months after the last dose of study drug. However, any SAEs volunteered by subjects after this time point must be reported according to standard procedures. All SAEs must be followed to resolution or, if resolution is unlikely, to stabilization. Any SAE judged by the investigator to be related to the study treatment or any protocol-required procedure should be reported to the sponsor regardless of the length of time that has passed since study completion.

The detailed contact information for reporting of SAEs is provided in the Investigator Study File.

For urgent safety issues, please ensure all appropriate medical care is administered to the subject and contact the appropriate study team member listed in the Investigator Study File.

It is very important that the SAE report form be filled out as completely as possible at the time of the initial report. This includes the investigator's assessment of causality.

Any follow-up information received on SAEs should be forwarded within 1 business day of its receipt. If the follow-up information changes the investigator's assessment of causality, this should also be noted on the follow-up SAE form.

Preliminary SAE reports should be followed as soon as possible by detailed descriptions including copies of hospital case reports, autopsy reports, and other documents requested by the sponsor.

The investigator must notify his/her IRB/IEC of the occurrence of the SAE in writing, if required by their institution. A copy of this communication must be forwarded to the sponsor, or its designee, to be filed in the sponsor's Trial Master File.

9.5.4.2 Reporting of Pregnancy and Exposure to Study Drug Through Breastfeeding

Any pregnancy in which the estimated date of conception is either before the last visit or within 28 days of last study treatment, or any exposure to study drug through breastfeeding during study treatment or within 28 days of last study treatment, must be reported.

If an adverse outcome of a pregnancy is suspected to be related to study drug exposure, this should be reported regardless of the length of time that has passed since the exposure to study treatment.

A congenital anomaly, death during perinatal period, an induced abortion, or a spontaneous abortion are considered to be an SAE and should be reported in the same time frame and in the same format as all other SAEs (see Reporting of Serious Adverse Events [[Section 9.5.4.1](#)]).

Pregnancies or exposure to study drug through breastfeeding must be reported by fax or email as soon as possible but no later than 1 business day from the date the investigator becomes aware of the pregnancy. The contact information for the reporting of pregnancies and exposure to study drug through breastfeeding is provided in the Investigator Study File. The Pregnancy Report Form must be used for reporting. All pregnancies must be followed to outcome. The outcome of the pregnancy must be reported as soon as possible but no later than 1 business day from the date the investigator becomes aware of the outcome.

A subject who becomes pregnant must discontinue study treatment.

